| PR | partial response |
| PVC | polyvinyl chloride |
| ORR | objective response rate |
| OS | overall survival |
| QT | cardiac interval from start of Q wave to end of T wave |
| RDC | remote data capture |
| RR | respiration rate |
| SD | stable disease |
| UGT | uridine-diphosphoglucuronosyltransferases |
| ULN | upper limit of normal |
| VADs | Vascular access devices |
| WHO | World Health Organization |

1. STUDY SYNOPSIS

| |
|---|
| 
Title of Study: Phase II trial of Nivolumab and Metformin in patients with treatment refractory MSS metastatic Colorectal Cancer
 |
| 
Study Centers: Emory University Winship Cancer Institute
 |
| 
Study Phase: Phase II
 |
| 
Objectives:
 
Primary Objective:
 
▪ The primary endpoint of this study is to Evaluate the effect of metformin in combination with nivolumab on the overall response rate (ORR) (Primary Objective) as assessed by RECIST.1.1 
Secondary Objectives:
 
▪ To determine the effect of the metformin and nivolumab combination on clinical (PFS, OS) outcomes and biochemical (CEA) response.▪ To compare the effect metformin and nivolumab combination on immune and metabolic biomarkers in the tumor microenvironment and systemic circulation (pre and post treatment paired biopsies required). |
| 
Trial Design/Methodology: Single arm phase II study. 28 patients with previously treated (previously treated with fluoropyrimidine, oxaliplatin, irinotecan and EGFR inhibitor – if RAS wildtype) metastatic CRC will be started on metformin and nivolumab combination.
 
Treatment
 
1. Patients will start taking metformin 500 mg po BID for 3 days, then 500 mg am and 1000 mg pm for 4 days, then 1000 mg po bid for 1 week. Patients of the study will get paired biopsies as outlined in study calendar.2. If a patient cannot tolerate metformin 1000 mg po BID the patient will resume the metformin dose which was tolerable3. After 2 weeks of metformin only therapy (lead-in period) patients will start nivolumab 480 mg IV q4 weeks and continue metformin 1000 mg PO BID (or the tolerated dose of Metformin).4. Restaging scans will be performed at the end of cycle 2, then every 8 weeks for 2 years.5. Correlative assays will include- immune profiling of TILs and circulating lymphocytes, plasma cytokine levels and metabolic biomarkers. These will be performed at baseline at baseline, cycle 1 day 1, cycle 1 day 15, Cycle 3 Day 1 and at progression 
Treatment regimen and trial diagram:
 |

Main criteria for exclusion:

- MSI status
- Autoimmune conditions that may require systemic steroids or other immunosuppressive treatments
- Pregnancy or breast feeding

Investigational product and administration:

Nivolumab will be provided intravenously and metformin will be provided in tablet form. Eligible subjects will receive nivolumab 480 mg IV every 4 weeks and metformin 1000 mg po BID according to the study design.

Control therapy, dose and administration: N/A

Efficacy evaluation/Endpoints:

Primary Endpoint: ORR

Secondary Endpoints: To determine PFS, OS, and biochemical response (CEA), immune and metabolic biomarkers in tumor microenvironment and systemic circulation (pre and post research biopsy required)

Safety evaluation/Endpoints:

[figure not shown]
NCI Common Toxicity Criteria Version 4.0

Rationale for number of subjects: Primary objective is to determine the overall response rate. Historically ORR with single agent nivolumab in CRC is <5% and metformin and nivolumab combination will have ORR of 15%. Simon's MinMax two stage design is employed for the study with power of 80% and alpha of 0.1. If there is 1 response in first 18 patients in the first stage of the study, then it will proceed with second stage to enroll total of 28 patients. If there are 3 or more responders out of the 28 patients then it would be positive study. This will enable us to evaluate clinical endpoints (ORR, CEA, RFS, OS) as well as evaluate the impact on immune biomarkers.

Statistical methods: Phase II design

Translational Research: Correlative assays will include- immune profiling of TILs and circulating lymphocytes, plasma cytokine levels, and key metabolic biomarkers of relevance to mechanism of metformin action when administered in combination with immunotherapy. Paired biopsies will be obtained in all patients.

2. TRIAL DIAGRAM

3. OBJECTIVES

3.1 Primary Objective and Hypotheses

1. **Objective:** To evaluate the effect of nivolumab and metformin combination on the overall response rate (ORR) as assessed by RECIST 1.1.

Hypothesis: Metformin will impact the tumor microenvironment and potentiate the anti-tumor effects of nivolumab in patients with treatment refractory, MSS metastatic CRC patients.

3.2 Secondary Objectives and Hypotheses

1. **Objective:** To determine the effect of nivolumab and Metformin combination on clinical outcomes, progression free survival and overall survival, and biochemical response (CEA).

Hypothesis: Metformin plus nivolumab will affect overall response rate, progression free survival, overall survival.

2. **Objective:** To compare the effect of nivolumab and metformin combination on immune and metabolic biomarkers in the tumor microenvironment and systemic circulation (pre and post treatment paired biopsies required).

Hypothesis: Metformin plus nivolumab will change the immune profile in the peripheral blood as well as the tumor microenvironment.

4. BACKGROUND AND RATIONALE

4.1 *Study Disease*

Colorectal cancer (CRC) is the third most common cancer in the US and it is estimated to cause more than 50,000 deaths in 2018. [1] Approximately 20% of patients have metastatic CRC at initial presentation who have a 5 year overall survival of 14%. [1] Clear majority of the CRCs develop through chromosomal instability (CIN) pathway and approximately 15% develop from the microsatellite instability (MSI) pathway which results from deficient DNA mismatch repair (MMR). [2] While about 15% of all CRCs are MSI-H, about 4% of metastatic CRCs are MSI-H. [3] Germline mutations in MMR genes such as MLH1, MSH2, MSH6, PMS2 or epigenetic inactivation of MLH1 gene cause deficient MMR. MSI-H CRCs have better stage adjusted prognosis compared to MSS CRCs. [2] Consensus molecular subtype (CMSs) system classifies CRCs into 4 different gene expression-based molecular subtypes: CMS1 (14%, microsatellite unstable with strong immune activation and hypermutated), CMS2 (canonical, 37%, epithelial differentiation, strong WNT and MYC Signaling activation), CMS3 (13%, characterized with metabolic dysregulation and KRAS mutations) and CMS4 (mesenchymal, 23%, phenotype with strong transforming growth factor beta activation, stromal invasion and angiogenesis), an unclassified group with mixed features represent 13% of remaining cases. [4] The immunological signatures of tumor microenvironment (TME) and the molecular subtypes were shown to be correlated. [Becht et al] CMS1 is the most immunogenic subtype of all four subtypes while the CMS4 is the second most immunogenic. [4, 5] Immunotherapy with checkpoint inhibitors has been proven to be very effective in the treatment of metastatic CRC with high level of Microsatellite Instability (MSI-H), but ineffective in Microsatellite Stable (MSS) CRC. [6] Immunotherapy with anti-PD-1 agents is approved only in MSI-H metastatic CRC patients after failure of standard first line systemic chemotherapy. [7] MSI-H tumors respond to check point inhibitors because of high mutational rate, up 20 times higher compared to MSS CRC, as well as significant immune checkpoint expression [5]. At the present time patients with MSI-H status, high expression of neo-antigens and TILs are good candidates for check point inhibition whereas MSS CRC patients lack response to immunotherapy due to opposite tumor features. [5] TME is essential for prognosis and is a viable target for anti-cancer therapy by modulation of the TME composition. Only a small set (4%) of metastatic CRCs would be candidate for anti-PD-1 therapy therefore there is significant unmet need for innovative approaches to combine anti-PD1 therapy with other agents to achieve manipulation of TME of CRCs and sensitize MSS CRCs to anti-PD-1 therapy. For example, by modulating the tumor microenvironment antitumor responses (ORR 17%, 4PR, 5SD) were reported in MSS patients when a checkpoint inhibitor was combined with Cobimetinib in a phase Ib trial based on preclinical data showing increased intratumoral CD8+ T cell infiltration and increased sensitivity to PDL-1 inhibition. [8] The preclinical rationale was also confirmed in this phase Ib trial by showing increased CD8+ T cell infiltration, MHC-I expression and PDL-1 upregulation in serial tumor biopsies on treatment.

4.2 *Investigational Agents*

4.2.1

Nivolumab in CRC:

Immune checkpoint expression as programmed death 1 (PD-1) or cytotoxic T-lymphocyte-associated antigen (CTLA-4) by tumor cells is one of the major immune evasion mechanisms. [3, 9] PD-1, a member of B7/CD28 costimulatory receptor family, down regulates T-cell activation by binding to its receptors programmed death ligand 1 (PD-L1) and programmed death ligand 2 (PDL-2). Nivolumab is a fully humanized monoclonal IgG4 anti-PD-1 inhibitor which is currently approved for MSI-H CRC after progression on systemic chemotherapy.

Nivolumab was studied as a single agent at doses of 0.3-10 mg/kg in the first phase I study in 39 patients with advanced solid tumors, 1/14 CRC patients achieved durable complete response (CR), no maximum tolerated dose was determined. [10] That patient had MSI-H positive CRC. In the following phase Ib study with single agent Nivolumab at a dose of 0.1-10 mg/kg IV in 296 patients with treatment refractory solid tumors none of the 19 CRC patients had objective response. Of note these patients included predominantly MSS CRCs. [11]

CheckMate 142 Phase II study of single agent Nivolumab 3 mg/kg IV every 2 weeks in 74 treatment refractory MSI-H CRC patients revealed 31.1% objective response rate (ORR), 3% complete response (CR) and 69% disease control rate (DCR) for 12 weeks or longer at a median follow up of 12 months. [12] More updated results of the same study at median follow up of 21 months revealed 34% ORR, 9% CR, and 62% DCR. [13] The response rates did not differ between Tumor expression of PD-L1 \geq 1% and <1% in the same study. CheckMate142 trial currently has multiple arms with Nivolumab combined with other agents.

Most commonly reported grade 3 or 4 adverse events in CheckMate142 study included elevated lipase (8%) elevated amylase (3%); and rest of grade 3 or 4 adverse events included fatigue (1%), diarrhea (1%), maculopapular rash (1%), increased alanine aminotransferase (1%), stomatitis (1%), abdominal pain (1%), increased creatinine (1%), decreased lymphocyte count (1%), colitis (1%), acute kidney injury (1%), adrenal insufficiency (1%), esophagitis (1%), increased gamma-glutamyltransferase (1%), gastritis (1%), pain (1%) No treatment related deaths were reported.

Please refer to the Investigator's Brochure for additional information for preclinical activity, toxicology and potential adverse effects.

4.2.2

Metformin in CRC:

Metformin is a biguanide and decreases liver glucose production and increases insulin sensitivity. It is the first line therapy and most commonly prescribed antidiabetic agent for diabetes mellitus type II. It has favorable safety profile, weight neutral effects, low risk of hypoglycemia and low cost. [14] Immediate release (IR) and extended release formulations (ER) exist and extended release formulation provides better tolerability especially lower gastrointestinal adverse events as well as improved patient adherence. ER formulation provides gradual release of the drug into upper GI tract although it provides similar drug exposure at the same daily total dose as immediate release formulation. [14] Maximum plasma concentration of IR Metformin is reached at 2-3 hours and 7 hours for ER Metformin. [15] ER tablets cannot be crushed or chewed and should be swallowed whole in order to maintain slow drug release. The most common adverse events were reported as following in a 16-week, randomized, double-blind, placebo-controlled study in patients with type II diabetes: upper respiratory tract

infection (15%), diarrhea (12.9%), nausea/vomiting (8.2%), musculoskeletal pain (7.6%), headache (7.1%), influenza (6.6%), dyspepsia/heartburn (5.3%), abdominal pain (5.1%), sinus abnormality (3.7%), dizziness (3.4%), hypertension (3.1%), urinary tract infection (3.1%). That particular study included 5 different treatment regimens including Metformin ER 1000 mg po twice daily.

Please refer to the Investigator's Brochure for additional information for preclinical activity, toxicology and potential adverse effects.

Several epidemiological studies revealed decreased risk of cancer development and cancer related mortality with use of metformin. A meta-analysis revealed decreased risk of colorectal cancer incidence diabetic patients who are on metformin and improved overall mortality, CRC specific mortality in CRC patients who are on metformin compared to those who are not. [16, 17] In meta-analysis by Meng et al. improved overall survival (OS), HR 0.75; 95% CI 0.65 to 0.87, was reported for metformin users compared to nonusers in patients with CRC and diabetes although no cancer specific survival, HR 0.79, 95% CI 0.58 to 1.08, was detected. [18] Anticancer properties of Metformin were attributed to mTOR inhibition through AMPK pathway activation. [19] The positive therapeutic effects of metformin were shown in colon cancer and lung cancer patients with diabetes on metformin versus other antidiabetic drugs in a single institution retrospective study. [20] In that study colon cancer (104 on metformin, 98 non-metformin) and lung cancer (93 metformin and 87 non-metformin) patients with diabetes were stratified according to being on metformin versus other antidiabetic medications between 1998 and 2012. 94.2% of patients were treated with surgery, 44.2% were treated with chemotherapy, and 14.4% were treated with radiation therapy in colon cancer patients on metformin as opposed to 89.8%, 48% and 18.4% in non-metformin cohort with colon cancer. In the colon cancer group better OS (5.7 versus 4.1 years, p=0.001), better 5-year OS rates (57% vs 37%, p=0.004), rate of CEA decrease (72% versus 47%, p=0.015), less metastasis (23% versus 46%, p=0.001), less number of deaths (48% versus 76%, p<0.001) and less recurrences (4% versus 19%, p=0.002) were seen in the metformin group compared to non-metformin group. Additionally, better 5-year OS rates (29% versus 15%. P=0.023) and OS (3.4 vs 1.8 years, p<0.001) were reported in patients on metformin compared to non-metformin antidiabetic medication group in lung cancer cohort. 48.4% received surgery, 47.3% received chemotherapy, and 40.9% received radiation therapy metformin cohort with lung cancer patients compared to 40.2%, 42.5%, 47.1% in non-metformin cohort, respectively. No clinical staging information was included for either colon cancer or lung cancer patients in this report. In a nationwide population-based study from Taiwan including 47,597 patients with DMII metformin use was associated with lower risk of CRC in a dose dependent manner. [21]

More recently multiple immunomodulatory effects of Metformin have been shown which points to potential synergistic effect of Metformin with anti-PD-1 therapy in CRC. [22, 23]

4.3 Study Rationale

Preclinical studies suggest that metformin, by virtue of its impact on metabolic features in the

tumor microenvironment has distinct immunomodulatory properties that could complement PD-1 blockade and may potentially increase the sensitivity of MSS metastatic CRC patients to PD-1 inhibition. [22, 23] Longer PFS and OS was reported in CRC patients with higher CD8+ T cell and memory T cell infiltration highlighting the potential role of immunomodulation as a mechanism by which metformin elicits its effects.

Immune effects of Metformin in tumor microenvironment:

1. Metformin increased CD8+ tumor infiltrating T cells (TILs) and prevented apoptosis and immune exhaustion of TILs. Metformin prevents apoptosis of CD 8+ tumor infiltrating lymphocytes (TILs) and restored multi-functionality of PD1+, Tim3+ CD8+ TIL by promoting a phenotypic switch of T cells to adopt central memory and effector phenotypes in murine tumor models. [22]
2. Metformin has metabolic properties that favor decreased intratumoral oxygen consumption in vitro and in vivo, while it increased the oxygen consumption by CD 8+ TIL and improved the effector cytokine production by CD8+ TIL in B16 melanoma and MC38 colon adenocarcinoma tumor models. [23]
3. Expression of coinhibitory molecules PD1 and Tim3 was modulated in metformin treated mice compared to controls. [23]
4. The combination of metformin and PD1 inhibitor resulted in improved intratumoral T cell function and increased anti-tumor activity. [23]
5. The metformin and PD-1 inhibitor combination improved antitumor activity and intratumoral T cell function. [23]

Preclinical data strongly suggests that metformin can improve immune exhaustion of TIL and potentiate the effects of immunotherapy. **Based on this preclinical rationale, in this study we propose evaluating the effects of metformin in potentiating the effects of immunotherapy in patients with treatment refractory metastatic MSS CRC patients.**

4.4 Correlative Studies Background

Abundant CD8+ T cell infiltration in the tumor microenvironment is associated with a survival advantage in CRCs, independent of tumor stage. [24] Individual molecular subtypes of CRCs have distinct immunological features. For example, CMS1 CRCs have upregulation of Th1 lymphocytes, cytotoxic T cells, NK cell infiltration and PD-1 expression. These features are correlated with better clinical outcomes in CRCs. [25] In contrast, tumors displaying an immune infiltration pattern with presence of Th17 cells, IL-17, Tregs, and MDSCs are associated with poorer outcomes in CRCs. [24, 26] Preclinical studies demonstrated that metformin could modulate the TME and improve CD8+ T cell infiltration and function, decrease tumor cell oxygen consumption and increase CD8+ T cell oxygen consumption. [22, 23] The current study aims to harness the immunomodulatory effects of metformin, and potential clinical benefit in combination with an anti-PD-1 agent, nivolumab, by modulating the cellular composition within the TME. Therefore, we aim to analyze the immunogenic profile of the tumors by paired biopsies and peripheral blood collection at the time points

specified in the protocol. In the paired pre and post-treatment biopsy specimens, we will aim to identify potential biomarkers for the combination therapy with Nivolumab and Metformin. Pre and post biopsy tissue will be evaluated using IHC or immunofluorescence for relevant lymphocyte, myeloid and stromal/vascular markers to provide a comprehensive view of the cellular composition within the TME. Tissue will also be dissociated and flow cytometry will be used to further define phenotypic properties of macrophages, lymphocytes or other cell populations. In addition, we plan to perform on a subset of these patients, genomic analysis of lymphocyte population.

Metformin is a mitochondrial electron transport chain Complex I inhibitor. The basis for co-administration of metformin with anti-PD-1 therapy relies on inhibiting Complex I activity in tumor cells, reducing oxygen consumption rates (OCR) in tumor cells while concomitantly increasing oxygen in the surrounding microenvironment and oxidative metabolism of the infiltrating T cell subsets. We will perform *ex vivo* studies to determine whether oxidative metabolism is indeed regulated in the tumor and T cell subsets. Pre and post therapy tumor sections will be evaluated for expression of the following: OCT-1 (metformin transporter), p-AMPK (that is known to be activated with metformin), mTOR pathway (should be suppressed as a consequence of AMPK activation), HIF1a, Caspase 3, and Ki67. Intracellular oxygen levels in tumor and stroma will be evaluated using HypoxyprobeTM to confirm OXPHOS inhibition. Sorted T cells populations will be evaluated for baseline OCR and OCR/ECAR (extra-cellular acidification) with and without short-term exogenous metformin administration using a Seahorse Bioenergetics bioanalyzer. In addition, viability of T cells with metformin or specific complex I inhibitors (rotenone/piericidin) will be evaluated. Glycolytic gene expression and OCT-1 expression in tumor samples prior to therapy and their correlation to therapy response can prospectively help define biomarkers of sensitivity to the combinatorial administration of metformin with anti-PD1. Evaluation of the outlined endpoints in pre- and post-treatment samples will help assess the biology of an anti-tumor response.

5. PATIENT SELECTION

5.1 Eligibility Criteria

- 5.1.1** Patients must have histologically or cytologically confirmed stage IV colorectal adenocarcinoma with measurable disease.
- 5.1.2** Prior treatment with 5 Fluorouracil (or capecitabine), oxaliplatin and irinotecan containing chemotherapy (needs to be treated with anti-EGFR agent if extended RAS wild type)
- 5.1.3** Patients must have measurable disease, defined as at least one lesion that can be accurately measured in at least one dimension (longest diameter to be recorded for non-nodal lesions and short axis for nodal lesions) as ≥ 20 mm with conventional techniques or as ≥ 10 mm with spiral CT scan, MRI, or calipers by clinical exam.

5.1.4 Age \geq 18 years.

5.1.5 ECOG performance status 0 or 1 (Karnofsky \geq 70%, see Appendix A).

5.1.6 Life expectancy of greater than 3 months

5.1.7 Patients must have normal organ and marrow function as defined below

- Absolute neutrophil count \geq 1,500/ μ L
- Platelets \geq 100,000/ μ L
- Hemoglobin \geq 9 g/dL or \geq 5.6 mmol/L without transfusion or erythropoietin (EPO) dependency (within 7 days of assessment)
- Serum creatinine \leq 1.5 x ULN

OR

creatinine clearance \geq 60 mL/min/1.73 m² for patients with creatinine levels $>$ 1.5 x ULN. Creatinine clearance should be calculated per institutional standard

- Serum total bilirubin \leq 1.5 x the upper limit of normal (ULN) OR direct bilirubin \leq ULN for subjects with total bilirubin $>$ 1.5 ULN
- AST(SGOT)/ALT(SGPT) \leq 2.5 \times institutional upper limit of normal
- Serum Albumin \geq 2.5 mg/dL
- International normalized ratio (INR) or prothrombin time (PT) \leq 1.5 x ULN unless subject is receiving anticoagulant therapy as long as PT or partial thromboplastin time (PTT) is
 - within therapeutic range of intended use of anticoagulants
 - Activated partial thromboplastin time (aPTT) \leq 1.5 x ULN unless subject is receiving anticoagulant therapy as long as PT or PTT is within therapeutic range of intended use of anticoagulants

5.1.8 Patients with diabetes mellitus should be on a stable diabetic treatment regimen for at least 1 month prior to trial enrollment and keep a blood glucose level log at home for the first 4 weeks of the trial.

5.1.9 Female subject of childbearing potential should have a negative urine or serum pregnancy within 72 hours prior to receiving the first dose of study medication; if the urine test is positive or cannot be confirmed as negative, a serum pregnancy test will be required.

5.1.10 Male subjects of childbearing potential must agree to use an adequate method of contraception, starting with the first dose of study therapy through 120 days after the last dose of study therapy.

- o Note: Abstinence is acceptable if this is the usual lifestyle and preferred contraception for the subject

5.1.11 Female subjects of childbearing potential must be willing to use an adequate method of contraception for the course of the study through 120 days after the last dose of study medication

- Note: Abstinence is acceptable if this is the usual lifestyle and preferred contraception for the subject

5.1.12 Ability to understand and the willingness to sign a written informed consent document.

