- 5.2.14** Has known active hepatitis B (e.g., hepatitis surface antigen [HBsAg] reactive) or hepatitis C (e.g., hepatitis C virus [HCV] ribonucleic acid [RNA] [qualitative] is detected).
- 5.2.15** Has received a live vaccine within 30 days of planned start of study therapy.
Note: Seasonal influenza vaccines for injection are generally inactivated flu vaccines and are allowed; however intranasal influenza vaccines (e.g., Flu-Mist) are live attenuated vaccines, and are not allowed

5.2.16 Uncontrolled intercurrent illness including, but not limited to, ongoing or active infection, symptomatic congestive heart failure, unstable angina pectoris or myocardial infarction within 6 months of study entry, serious cardiac arrhythmia requiring medications, baseline corrected QT (QTc) >450 msec or previous history of QT prolongation while taking other medications.

5.2.17 Other medications, or severe acute/chronic medical or psychiatric condition, or laboratory abnormality that may increase the risk associated with study participation or study drug administration, or may interfere with the interpretation of study results, and in the judgment of the investigator would make the subject inappropriate for entry into this study

5.2.18 Has a known additional malignancy that is progressing or requires active treatment; exceptions include basal cell carcinoma of the skin or squamous cell carcinoma of the skin that has undergone potentially curative therapy or in situ cervical cancer. Subjects with prior malignancies are eligible if the subject has been disease free for >5 years.

5.2.19 Is pregnant or breastfeeding, or expecting to conceive or father children within the projected duration of the trial, starting with the screening visit through 120 days after the last dose of trial treatment.

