8.1.5.1 Screening

Screening Period

All subjects must sign an informed consent document prior to the initiation of any study related procedures. The informed consent document must be signed within 28 days of Cycle 1 Day 1. Screening procedures are to be conducted within 28 days of Cycle 1 Day 1.

- Review of study eligibility criteria
- Medical History
- Record concomitant medications taken up to 28 days prior to day 1 cycle 1
- Vitals [temperature, heart rate (HR), blood pressure (BP) and respiratory rate (RR)]
- Physical Examination, including height and weight
- ECOG Performance Status evaluation (within 14 days or less of cycle 1 day 1)
- Laboratory Assessments

- Hematology: hemoglobin, hematocrit, red blood cell count, white blood cell count with differential and platelet count
- Serum chemistry: sodium, potassium, chloride, bicarbonate, magnesium, calcium, phosphorus, blood urea nitrogen, creatinine, total bilirubin, LDH, total protein, ALP, ALT, AST, and albumin. Fasting triglycerides, cholesterol and glucose.
- Serum or urine pregnancy test for women of childbearing potential. Must be within 72 hours of study drug
- Prothrombin time (PT) and activated partial thromboplastin time (aPTT)
- Urinalysis
- Tumor markers: CEA
- T3, FT4, TSH
- 12-lead ECG
- Radiologic imaging studies to evaluate tumor status. contrast computed tomography (CT) or magnetic resonance imaging (MRI) of the chest and abdomen and pelvis. Additional imaging may be obtained as clinically indicated. Baseline scans may be done within 4 weeks prior to cycle 1 day 1.
- Baseline fresh biopsy (in all patients, 28 total) will be obtained within 28 days of day 1 cycle 1 and after consent is signed.
- Blood sample 20 cc for correlative work

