8.1.7.2 Second Course Phase (Retreatment Period)

Subjects who stop nivolumab/metformin with SD or better may be eligible for up to one year of additional nivolumab/metformin therapy if they progress after stopping study treatment. This retreatment is termed the Second Course Phase of this study and is only available if the study remains open and the subject meets the following conditions:

- **Either**

- Stopped initial treatment with nivolumab/metformin after attaining an investigator-determined confirmed CR according to RECIST 1.1, and
 - Was treated for at least 24 weeks with nivolumab/metformin before discontinuing therapy
 - Received at least two treatments with nivolumab/metformin beyond the date when the initial CR was declared

OR

- Had SD, PR or CR and stopped nivolumab/metformin treatment after 24 months of study therapy for reasons other than disease progression or intolerance

AND

- Experienced an investigator-determined confirmed radiographic disease progression after stopping their initial treatment with nivolumab/metformin

- Did not receive any anti-cancer treatment since the last dose of nivolumab/metformin
- Has a performance status of 0 or 1 on the ECOG Performance Scale
- Demonstrates adequate organ function as detailed in Section 5.1.7
- Female subject of childbearing potential should have a negative serum or urine pregnancy test within 72 hours prior to receiving retreatment with study medication.
- Female subject of childbearing potential should be willing to use 2 methods of birth control or be surgically sterile, or abstain from heterosexual activity for the course of the study through 120 days after the last dose of study medication (Reference Section 5.1.10). Subjects of child bearing potential are those who have not been surgically sterilized or have been free from menses for > 1 year.
- Male subject should agree to use an adequate method of contraception starting with the first dose of study therapy through 120 days after the last dose of study therapy.
- Does not have a history or current evidence of any condition, therapy, or laboratory abnormality that might interfere with the subject's participation for the full duration of the trial or is not in the best interest of the subject to participate, in the opinion of the treating investigator.

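### The serum albumin eligibility limit in Section 5.1.7 is written in mg/dL, so as written it screens out nobody

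*Combined protocol and SAP*

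**What the plan says.** Section 5.1.7 opens its list of laboratory limits with "Patients must have normal organ and marrow function as defined below". The albumin entry is "Serum Albumin \geq 2.5 mg/dL". The hemoglobin entry in the same list is in grams per decilitre, with a molar equivalent: "Hemoglobin \geq 9 g/dL or \geq 5.6 mmol/L without transfusion".

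Albumin is measured at screening as part of the serum chemistry (Section 8.1.5.1: "total bilirubin, LDH, total protein, ALP, ALT, AST, and albumin"). It appears again among the chemistry tests at the treatment visits and in Table 5. None of these places gives a unit, a reference range or another threshold, so Section 5.1.7 holds the only albumin limit in the documents.

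The limit is used a second time. For the Second Course Phase, Section 8.1.7.2 requires that the patient "Demonstrates adequate organ function as detailed in Section 5.1.7".

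Separately, exclusion 5.2.17 lets the investigator turn away a patient with a "laboratory abnormality that may increase the risk associated with study participation or study drug administration". Section 8.1.7.2 has a similar discretionary clause for retreatment. Neither names albumin.

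**The concern.** A lower limit can exclude a patient only if some patients fall below it. Serum albumin is ordinarily present in grams per decilitre, and a limit of a few milligrams per decilitre lies far below that scale. The line looks like a unit slip in an operative eligibility criterion, not in background text.

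What is at stake is a fixed, checkable threshold. Section 8.1.1.2 has staff review every criterion, and Section 11.5 has the principal investigator or a co-investigator review eligibility for each new patient. Section 11.5 also allows monitors to verify it. All of them check against this line. Read literally, it never fails. Read as g/dL, it is a different criterion from the one approved. Two people could classify the same patient differently, and the text would not settle which was right.

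**Working it through.** The limit is a stated threshold, not a derived figure, so there is no plan calculation to reproduce. The check is a unit conversion.

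**Inputs**
- Albumin limit: 2.5 mg/dL (Section 5.1.7).
- Hemoglobin limit: 9 g/dL, paired with 5.6 mmol/L (Section 5.1.7).
- Serum albumin scale: not in the documents. Assumed, deliberately wide, to be 0.5 to 5.0 g/dL.
- Hemoglobin monomer mass: not in the documents. Assumed to be 16.114 g/mmol, and used only to check the neighbouring line.

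**Step 1. Convert the written limit.** 2.5 mg/dL ÷ 1000 mg/g = 0.0025 g/dL = 0.025 g/L.

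**Step 2. Compare it with the assumed range.** Multiple of the limit = (albumin in g/dL × 1000) ÷ 2.5. The last column shows what would follow if the numeral were kept and the unit were g/dL.

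| Albumin (g/dL) | In mg/dL | Multiple of written limit | Passes as written | Passes at 2.5 g/dL |
|---|---|---|---|---|
| 0.5 | 500 | 200 | yes | no |
| 1.0 | 1000 | 400 | yes | no |
| 1.5 | 1500 | 600 | yes | no |
| 2.0 | 2000 | 800 | yes | no |
| 2.5 | 2500 | 1000 | yes | yes |
| 3.5 | 3500 | 1400 | yes | yes |
| 5.0 | 5000 | 2000 | yes | yes |

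Every value passes as written. The lowest is still 200 times the limit, so the result does not depend on where in the range patients lie.

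**Step 3. Check whether the text was damaged in reading.** The other units in the list are intact. The hemoglobin line also agrees with itself: 9 g/dL = 90 g/L, and 90 ÷ 16.114 = 5.59 mmol/L, against the stated 5.6. Damage to the albumin unit alone is unlikely.

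**Step 4. Look for a correction elsewhere.** Every other mention of albumin is as a test to be run, without a unit. Nothing overrides Section 5.1.7, and Section 8.1.7.2 imports it unchanged.

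**The case against.** The strongest reply is that the slip does little harm. This is a single-centre trial. Staff comparing a laboratory result in g/dL (an assumption, since no reporting unit is given) with a limit of 2.5 would probably apply the numeral as if it were in g/dL. That stands, and it is why the practical effect is probably small. It does not make the line right: those staff would be applying a limit the protocol does not state.

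Three stronger readings are tempting, and the documents support none of them.

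- **A reader might infer that patients with low albumin cannot be refused.** Exclusion 5.2.17 allows refusal for a laboratory abnormality that raises risk, and Section 8.1.7.2 has its own clause for retreatment. Other criteria also limit bilirubin, transaminases, coagulation and performance status, and require a life expectancy of more than 3 months. What is missing is a numeric albumin limit, not all protection.
- **A reader might infer that the slip lets in patients who leave before the first scan and count as non-responders.** The documents do not say why albumin is limited or link it to early withdrawal. The handling of early leavers is not uniform either. Sections 6.12 and 8.1.1.6 replace some as inevaluable, while Section 10.3 counts unassessable eligible patients as failures.
- **A reader might infer that the primary analysis is compromised.** Section 10.3 bases conclusions on eligible patients, so an ambiguous criterion could make one patient's status arguable. But Section 10.4 includes everyone who receives any study drug, and nothing shows that an affected patient would enrol. The criterion does not enter the sample size calculation.

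**Conclusion.** The concern holds as a unit error in an operative eligibility criterion. As written, the limit is 0.0025 g/dL and excludes nobody at enrolment or at retreatment. This rests on one assumption from general knowledge, that serum albumin lies in the gram-per-decilitre range, and it holds across the whole span of 0.5 to 5.0 g/dL.

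If the numeral is right and only the unit is wrong, the written limit is too low by a factor of exactly 1000. The hemoglobin line makes g/dL the likely unit but does not prove it, or prove that 2.5 is the intended value. The documents do not show how many patients would be classified differently. Sample size and error rates are unaffected. This is a minor correction, but a clear one.

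**What to change.** The sponsor should confirm the intended unit and value of the albumin limit together, then correct the entry in Section 5.1.7. If the unit is confirmed as g/dL, it will match the hemoglobin entry "Hemoglobin \geq 9 g/dL" in the same list. Section 8.1.7.2 needs no edit, because it takes its limits from 5.1.7 by reference. The screening form and any eligibility checklist should carry the same unit.

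The cost is a correction to one line, which can go into the next amendment. No design parameter or analysis needs to be reworked.
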